11.7 Functional Performance Testing: (Visits 2, 5, 6)

Measures of functional performance will include 6 min walk test (6MW), timed-up-and-go test (TUG), and 4-meter walk (4mW) tests³⁸⁻⁴⁰. The 6MW test measures the distance walked in 6 minutes. This test was developed and used extensively to measure endurance. The test has been validated to measure functional mobility following knee arthroplasty. The 6MW test has been demonstrated to have excellent test-retest reliability, with intra-class correlation coefficients from 0.95-0.97, and a low coefficient of variation (10.4%)^{41,42}. The 6MW test is safe, easy to administer, well tolerated, and does not require extensive patient training³⁸⁻⁴⁰.

The timed up and go TUG measures the time it takes a patient to rise from an arm chair (seat height of 46 cm), walk 3 m, turn and return to sitting in the same chair without physical assistance⁴³. This test has excellent reliability as measured in a group of 60 functionally disabled older adults (mean age 80 years)⁴³. The 4MW will be assessed at the fastest safe speed for each participant. This test assesses the capacity for performance of certain activities (e.g. crossing a street before the light changes). The time it takes for each participant to ascend and descend 9-12 stairs will be measured which will assess joint strength, stability and agility.

This measure was selected because it has been shown to predict risk of physical disability, higher health care utilization and increased mortality⁴⁴⁻⁴⁶. It has been established as a meaningful outcome measure in older persons with a wide range of conditions⁴⁷⁻⁴⁹. Additionally, it is a valid and reliable measure⁵⁰⁻⁵²; and is well tolerated by patients varying in condition and degree of health^{53,54}.

11.8 Lower-Extremity Kinematics, Video-Motion Analysis:**(Visits 2, 5, 6)**

Video-motion analysis can assess even subtle changes in musculoskeletal function due to limited joint range of motion, stiffness, pain and/or weakness. Subjects will be equipped with a full-body retro-reflective marker set (including four-marker thigh and shank clusters on each leg). Kinematics measurements will be captured with a video-motion analysis system consisting of 18 infrared, 12-megapixel motion capture cameras (Oqus 7, Qualisys AB, Gothenburg, Sweden). Ground reaction forces will be acquired simultaneously using an instrumented treadmill or force plates (Bertec, Columbus, OH). Angular kinematics and net joint moments will be determined for the trunk, pelvis, hips, knees and ankles using Visual3D software (C-Motion, Inc., Germantown, MD). Tasks will include treadmill gait (1 m/s) and a 4-step stair ascent/descent.

11.9 Assessment of Muscle Strength, Isokinetic Dynamometry:**(Visits 2, 5, 6)**

The isokinetic muscle test will involve the use of the HUMAC NORM Isokinetic testing system (Computer Sports Medicine Inc, Stoughton, MA)⁵⁵. Participants will sit in the chair and press their leg against a padded bar as hard as they can while moving their leg back and forth (flexing and extending). They will do this at one speed (60°/s) with three repetitions at each speed for both the left and right leg. This will allow measurement of muscle activity surrounding the knee joint and the amount of force they can produce. Participants will be given a warm-up period (5 minutes walking or cycling), practice trials, and adequate rest time between repetitions (30 sec) and between left/right sides (5 min). As is standard practice when using the HUMAC NORM system, padded straps will be used on the participant's torso and legs in order to isolate the lower leg movements and reduce the contribution of other muscles. All measurements will be normalized to % body weight.

12.0 Study Management of Adverse Events

12.1 Definition

An adverse event (AE) is any untoward medical occurrence in a subject administered a Study Medication and which does not necessarily have a causal relationship with this treatment. An AE can therefore be any unfavorable and unintended sign (including an abnormal laboratory finding), symptom, or disease temporally associated with the use of whether or not related to the Study Medication (ICH E2A II/A/1, 21 CFR 312.32).

All pre-existing medical conditions will be recorded on the medical history study document. Starting with the administration of the Study Medication any new experience that was not present at baseline or worsening of an event present at baseline in intensity or frequency, is considered an adverse event.

Note: Unchanged, chronic conditions are NOT adverse events and should not be recorded.

It is recognized that subjects will exhibit (throughout follow-up) symptoms of the underlying disease process of that fluctuates in severity and duration.

Adverse events will include those occurrences, which when compared to before treatment meets any of the following criteria:

- Represent a new event or escalation of an event;
- Require a new escalation in treatment;
- Lasts longer;
- Experienced more frequently;
- More intense;
- Different in character (e.g. stabbing vs. ache);
- Experienced in a different part of the body; and/or
- Brought on by activity that previously did not cause the symptom.

12.2 Recording Adverse Events

Adverse events that occur during Study Medication administration will be recorded. Terms should be recorded consistently, using acceptable medical terms. When possible, a diagnosis should be identified as the AE (i.e., disease or syndrome) rather than the component signs and symptoms, and recorded on the case report form (e.g., record congestive heart failure rather than dyspnea, rales and cyanosis). However, signs and symptoms considered unrelated to encountered syndromes or diseases are to be recorded as individual AEs (e.g., if congestive heart failure and severe headaches are observed at the same time, each experience is to be recorded as an individual AE). The AE should not be recorded as a procedure or clinical measurement (i.e., a laboratory or vital sign) but should reflect the reason for the procedure or diagnosis.

Death is considered to be an outcome of an AE. The cause of death (rather than the term “death”) should be recorded on the serious AE and death report case report forms.

Subjects should be encouraged to report AEs spontaneously or in response to general, non-directed questioning. At each required visit (or whenever reported) during the study, all AEs that have occurred since the previous visit must be recorded on the AE case report form.

All AEs, regardless of seriousness, severity, or presumed relationship to the treatment must be recorded using medical terminology.

All AEs must be followed until resolution or until a stable clinical endpoint is reached. All measures required for AE management and the ultimate outcome of the AE must be recorded in the study document. All adverse events that occur in the study population will be tabulated and summarized.

12.2.1 Date of Onset and Resolution

The date of onset is the time at which the subject reports that the incident began. This may or may not be the date on which the Study Team became aware of the event. The date of resolution is the date at which the event was no longer apparent to the subject and/or the Study Team. This may be unknown if at the end of the study the event is not resolved. In this case, the event will be indicated to be unresolved.

12.2.2 Incidence

An AE may be classified as “intermittent” or “continuous if has no periods of abatement.

12.2.3 Relationship to Study Medication

The Principal Investigator is required to assess whether there is a reasonable possibility that the Study Medication caused or contributed to an AE.

Many terms and scales are used to describe the degree of causality between a Study Medication and an event. The expression “reasonable causal relationship” is meant to convey in general that there are facts (evidence) or arguments to suggest a causal relationship (ICH E2A, III/A/1).

Determination of whether there is a reasonable possibility that a treatment caused or contributed to an AE includes assessing temporal relationships, biologic plausibility, association (or lack of association) with underlying disease, and presence (or absence) of a more likely cause.

As is recommended in FDA draft guidance document, Safety Reporting Requirements for INDs and BA/BE Studies (2010), we define four degrees of relatedness: “unrelated”, “probably not related”, “suspected adverse drug reaction” (SADR) or “adverse reaction”.

Unrelated (clearly not related to the research)

The occurrence of the AE is not reasonably related in time, OR the AE is considered unlikely to be related to the treatment (biologically implausible).

Probably not related (doubtfully related to the research)

The administration of the treatment and the AE are not considered reasonably related in time AND the AE could also be explained by causes other than the treatment (concurrent illness/underlying disease, other drugs or procedures).

Suspected Adverse Drug Reaction (SADR)

Suspected adverse reaction means any AE for which there is a reasonable possibility that the treatment caused the AE. A ‘reasonable possibility’ means there is evidence to suggest a causal relationship between the treatment and the AE. A SADR reaction implies a lesser degree of certainty about causality than adverse reaction, which means any AE caused by a treatment.

The Principal Investigator should consider if exposure to the treatment and the AE are reasonably related in time AND the treatment is more likely than other causes to be responsible for the AE or is the most likely cause of the AE.

Adverse Reaction

An adverse reaction means any adverse event caused by a drug. Adverse reactions are a subset of all suspected adverse reactions for which there is reason to conclude that the treatment caused the event.

If the event is felt by the Principal Investigator to be either a SADR or an adverse reaction, every effort will be made to identify the event as related to the Study Medication. Adverse events that are generally felt to be attributable to the Study Medication occur in close temporal relationship to the onset of dosing. A discussion of AEs that are common with the Study Medication is found in the **Section 13.0** of this document.

All adverse reactions and SADRs will be followed until resolution or the Investigator judges the experience to be chronic or stable.

12.2.4 Severity (Intensity) of Adverse Events

The severity of the adverse events should be assessed based on the following grading scale:

- Grade 1 (Mild): Adverse event that is noticeable to the subject and may require additional therapy;
- Grade 2 (Moderate): Adverse event that interferes with the subject’s activities and requires intervention or additional therapies;
- Grade 3 (Severe): Adverse event that is intolerable, or necessitates additional therapy or places the subject at immediate risk of harm;
- Grade 4: Adverse event that is life-threatening or disabling (hospitalization);
- Grade 5: Adverse event that results in Death.

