12.3 Reporting of Adverse Events

12.3.1 Function of the Medical Monitor and FDA

An Independent Medical Monitor will be selected to oversee study safety. A detailed medical Monitoring plan will be submitted to FDA upon appointment of this individual and before the first subject is treated. This individual is to be an appropriately certified physician experienced in monitoring clinical trials.

The Principal Investigator will be responsible for confirming the severity of all adverse events. All serious events will be reported to the Independent Medical Monitor within 24 hours of their disclosure to the Principal Investigator. The Medical Monitor will review data or events reported by the Study Team within 72 hours of disclosure to the Medical Monitor.

During this time, appropriate care will be given to the study subject. If managing adverse events requires unblinding to the any member of the Study Team, the appropriate team member will disclose the group identity to the necessary medical provider.

The IRB will be notified of unanticipated and serious adverse events within 5 business days of identification. This reporting may come from the Study Team, the Independent Medical Monitor, or both.

Investigator Sponsor will notify FDA in an IND safety report (Form 3500A), unexpected fatal or life threatening suspected adverse reactions where there is evidence to suggest a causal relationship between the Study Medication and the adverse event will be reported as a serious suspected adverse reaction. This will be reported to the FDA no later than 7 calendar days after the sponsor-investigator's initial receipt of the information about the event.

Other unexpected serious suspected adverse reactions, where there is evidence to suggest a causal relationship between the Study Medication and the adverse event, will be reported as a serious suspected adverse reaction. This will be reported to the FDA on FDA Form 3500A no later than 15 calendar days after the sponsor-investigator's initial receipt of the information.

The sponsor must identify all IND safety reports previously submitted to FDA concerning a similar suspected adverse reaction and must analyze the significance of the suspected adverse reaction in light of previous, similar reports or any other relevant information.

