13.8 Associated with Motion Capture

There is a small risk of skin irritation from the tape used to attach the reflective markers. The tasks performed during motion capture are activities of daily living and therefore would place the participants at minimal risk for additional injury.

If skin irritation occurs, they will be instructed to apply over-the-counter anti-inflammatory creams, ointment or spray of their choice to the skin. In addition, to avoid injury subjects will be coached to take rest periods if needed and/or discontinue motion at any time during the evaluation.

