13.11 Risk Analysis

The Study Team will perform regular review of cumulative adverse events and will modify mitigation strategy as necessary. Baseline risk analysis is shown in **Table 13.11** below. It is intended that risks with higher overall risk score will be subject to greater and more frequent scrutiny and discussion of mitigation. As the study progresses, modifications to this analysis will be fully document and retained.

Table 13.11 Risk Analysis

Risk	Likelihood of Occurrence 1= not likely 2= possible 3= very likely	Potential Impact on Subject Safety 1=little 2= moderate 3= severe	Detectability 1= high 2= moderate 3= low	Overall Risk Score (Hierarchy of assessment and follow-up) (3-9)
Associated with FIS Administration	2	3	2	7

Associated with Placebo Administration	1	1	3	5
Associated with MRI	2	1	1	4
Associated With PRO Questionnaires	2	1	1	4
Associated With Physical Exam	2	1	1	4
Associated With Blood Draw	2	2	1	5
Associated With Isokinetic Muscle Strength Testing	2	1	1	4
Associated with Functional Performance Testing	2	1	1	4
Associated With Motion Capture	2	1	1	4
Associated with Breach of Confidentiality	2	2	2	6

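### Two classification rules in the primary safety comparison do not work as written: Grade 3 overlaps the lower grades on additional therapy, and Probably not related lies wholly inside Unrelated

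*Combined protocol and SAP*

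**What the plan says.** **Severity (12.2.4).** Grade 1 is an "Adverse event that is noticeable to the subject and may require additional therapy". Grade 2 is an event that interferes with the subject's "activities and requires intervention or additional therapies". Grade 3 is an "Adverse event that is intolerable, or necessitates additional therapy or places the subject at immediate risk of harm". Grades 4 and 5 cover life-threatening or disabling events and death. No rule says which grade applies when more than one fits.

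**Relatedness (12.2.3).** There are four classes. The heading of the first is glossed as clearly not related, and its definition is: "The occurrence of the AE is not reasonably related in time, OR the AE is considered unlikely to be related to the treatment", with a qualifier about biological implausibility. The second, Probably not related, is glossed as doubtfully related. It requires that event and treatment are not reasonably related in time and that something other than treatment could explain the event. The other two classes are suspected adverse drug reaction (SADR) and adverse reaction.

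**Who decides (12.3.1).** "The Principal Investigator will be responsible for confirming the severity of all adverse events".

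**Where it is used.** Section 15.5.1 lists severity and relatedness among the characteristics on which adverse events are compared between arms. The primary endpoint itself (8.2.1) is the occurrence of adverse events.

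**The concern.** A scale used to compare two arms should place each event in one class by a rule that another assessor could repeat. Neither scale does so. On severity, needing additional therapy appears in all three lower grades, and in Grade 3 it stands alone. This is a routine feature of the events concerned, because 12.1 counts a new escalation in treatment among the criteria for an adverse event. On relatedness, the class meant to express less certainty carries the stricter test. If the rules were followed literally, the breakdowns by severity and by four-class relatedness would reflect an unwritten convention chosen by the assessor and not the protocol.

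**Working it through.** No figure in the plan needs reproducing. The check sets the definitions side by side as conditions.

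**1. Severity.** For a noticeable event, let *I* = interferes with activities, *T* = needs additional therapy, *V* = needs another intervention, *X* = intolerable, *R* = immediate risk of harm. From 12.2.4:

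- Grade 1: noticeable, therapy optional
- Grade 2: *I* and (*V* or *T*)
- Grade 3: *X* or *T* or *R*

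For a tolerable event without immediate risk, *X* and *R* are false and Grade 3 reduces to *T*. Typical cases:

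| Event (noticeable, tolerable, no immediate risk) | Grade 1 | Grade 2 | Grade 3 |
|---|---|---|---|
| Needs therapy, does not interfere | fits | no | fits |
| Interferes and needs therapy | fits | fits | fits |
| Interferes, needs only another intervention | fits | fits | no |

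Every such event that needs therapy meets Grade 3 and at least one lower grade. Section 13.8 supplies an example: for skin irritation from marker tape, "they will be instructed to apply over-the-counter anti-inflammatory creams, ointment or spray of their choice to the skin". If the cream counts as additional therapy, that event fits the Severe wording as well as the Mild wording.

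Two possible repairs can be tested against the same conditions.

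- *Delete the therapy limb from Grade 3.* The grades still overlap. A Grade 2 event is still noticeable and so meets Grade 1. An intolerable event that interferes and needs therapy meets Grades 2 and 3. Immediate risk of harm in Grade 3 still overlaps life-threatening in Grade 4.
- *Apply the highest grade that fits, leaving the wording alone.* This gives a unique grade, but every event needing additional therapy becomes at least Severe. Grade 2 keeps only interfering events that need some other intervention.

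So the wording and the tie-break both need attention.

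**2. Relatedness.** Let *A* = not reasonably related in time, *B* = unlikely or implausible, *C* = another cause could explain the event. From 12.2.3:

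- Unrelated: *A* or *B*
- Probably not related: *A* and *C*

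(*A* and *C*) implies *A*, and *A* implies (*A* or *B*). Every event that meets Probably not related therefore also meets Unrelated, and none belongs to Probably not related alone. Reading the implausibility qualifier strictly, or ignoring *B* altogether, changes nothing, because *A* by itself is sufficient for Unrelated. Conversely, an event that is close in time but has a competing cause, a natural candidate for doubtfully related, cannot enter that class.

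**3. Which results depend on this.**

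- *Occurrence of any adverse event (8.2.1):* uses neither scale. Not affected.
- *Related versus not related:* 12.2.3 treats SADR and adverse reaction together as related, and both overlapping classes fall on the other side. Not affected by the overlap.
- *Seriousness (12.2.6) and expedited reporting to FDA (12.3.1):* defined without the severity grade and without distinguishing the two not-related classes. Not affected.
- *Severity breakdown and four-class relatedness breakdown (15.5.1):* affected.

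**4. Recording period.** The first sentence of 12.2 speaks of events during administration of study medication. The rest of 12.2 requires all events since the previous visit, or whenever reported. Section 12.1 starts collection at first administration and gives no end. The synopsis, 10.3 to 10.5 and the schedule in Appendix B place adverse-event review at the follow-up visits. The first sentence is out of line with text that already governs.

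**The case against.** The strongest reply is that these are wording faults with little practical effect. An experienced investigator reads a severity scale as ascending. One person confirms all grades, so variation between assessors is limited. Assessors are blinded (6.1), so misgrading should not favour either arm. Section 15.5.1 names Fisher's exact test for yes/no endpoints and Poisson or negative binomial regression for counts, and it names no four-class test. Most of this stands, and it limits the consequence. It does not supply the missing rule: a single assessor still has no written basis for choosing between two grades that both fit, and 15.5.1 does list severity and relatedness among the comparisons.

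Several stronger inferences are tempting, but the documents do not support them.

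- *That adverse events after dosing go unrecorded.* The first sentence of 12.2 does not say that only events during administration count. Mandatory wording in the same section and the visit schedule override it. Section 12.2 also requires events to be followed to resolution or a stable endpoint.
- *That Grade 2 lies wholly inside Grade 3.* It does not, because a Grade 2 event needing only another intervention stays outside.
- *That the risk table contradicts the grading.* The row "Associated With Motion Capture" in Table 13.11 scores potential impact on subject safety, which is not an adverse-event grade.
- *That termination of enrolment under 14.1 fails.* That section is discretionary. It does turn on whether an event can be determined to be unrelated, so it should be reconciled with 12.2.3, but it need not be invoking the formal class.

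**Conclusion.** The point holds for two rules. In 12.2.4, a tolerable, low-risk event that needs additional therapy fits Grade 3 and a lower grade, with no tie-break. In 12.2.3, Probably not related is a logical subset of Unrelated and has no members of its own. Both follow from the definitions as worded and need no outside figure. The effect is confined to the severity and four-class relatedness breakdowns of the primary safety comparison. The number of events concerned cannot be estimated, because the plan gives no expected adverse-event counts and no share needing therapy. The view that bias towards one arm is unlikely assumes that grading stays blinded; 12.3.1 allows disclosure where managing an event requires it. This should be fixed, but it does not undermine the primary endpoint as such. The first sentence of 12.2 is a minor editorial matter.

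**What to change.** Before unblinding, and preferably before the Group A and Group B labels described in 15.8 are attached:

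1. **Severity.** Reconcile how Grades 1 to 3 treat additional therapy, and state one rule for an event that fits more than one grade. Removing the therapy limb from Grade 3 is not sufficient on its own.
2. **Relatedness.** Redefine Probably not related so that it does not fall inside Unrelated. State how that class relates to the wording on unrelated events in 14.1. The sponsor must reconcile the two sections; this review does not propose the stopping criterion.
3. **Events already on file.** If any adverse events have been recorded, apply the revised definitions to them, blinded.
4. **Editorial.** Align the first sentence of 12.2 with the rest of 12.2, 12.1 and the schedule.

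The cost is a protocol amendment with IRB review, submitted to FDA as appropriate (16.2, 18.7), and updated guidance for the adverse-event form. Some blinded re-grading may be needed, and it may be limited by the source detail that was captured. No new visits or procedures are required.
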